In Part 3, the RBA and FE (Cohort 7) will include a randomized, open-label, single dose, 3-period crossover design to compare the RBA of single doses of the GSK3739937 PiB with GSK3739937 Tablet, and to assess the effect of food (fasted or fed (under moderate calorie and fat conditions)) upon the safety, tolerability and PK of the GSK3739937 Tablet ([Figure 2](#)). All doses will be administered immediately following a standardized meal for each dosing period that contains approximately 600 calories with approximately 30% of calories from fat (unless otherwise indicated in Part 3 dosing in fasted condition).

A summary of the overall study design, including doses, sample size, and order, is presented in [Figure 1](#) and [Figure 2](#) below.

Figure 1 Phase 1 Study in Healthy Participants using planned doses of VH3739937 Part 1 and Part 2

[figure not shown]
A=Active; P=Placebo

QD = once daily; QW = once weekly

*= Period 4 may include participants from both Cohorts 1 and 2

Highlighted cohorts and treatment periods denote completed

Figure 2 Phase 1 Study in Healthy Participants using planned doses of VH3739937 Part 3

Note: The doses shown in Figure 1 above are intended to demonstrate general concepts relating to factors of escalation. The modelling and simulation implemented using the data currently available following oral administration of a suspension formulation in the fed state indicated the predicted efficacious dose for the daily dose is 25 mg and the weekly dose is 500 mg. Due to the observed half-life of ~90 h, the anticipated accumulation ratio following repeated daily and weekly doses is ~ 6-fold and 1.3-fold, respectively. Dosing will be conducted in accordance with PK stopping criteria.

In Part 1, dose escalation will be determined by the Dose Escalation Committee (ViiV Healthcare (VH)/GlaxoSmithKline (GSK) study team and the Principal Investigator (PI))

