- Any changes in the timing or addition of time points for any planned study assessments, or changes in the duration and schedule of dosing and the doses to be administered in the SAD and MAD cohorts, as the result of emerging PK data from this study, must be documented and approved by the relevant study team member and then archived in the sponsor and site study files but will not constitute a protocol amendment.

Table 1 Screening and Follow-Up Assessments (Part 1, Part 2, and Part 3)¹

Procedure	Screening (up to 28 days before Day 1)	Follow-Up ² (approx. 28 days post last dose)	Notes
Outpatient Visit	X	X	
Informed Consent	X		
Inclusion/Exclusion Criteria and Demography	X		
Medical/medication/drug/alcohol history	X		
Full Physical Examination	X	X	A Full Physical Exam will include at a minimum, assessments of the Skin, Cardiovascular, Respiratory, Gastrointestinal and Neurological systems
SARS CoV-2 Testing ²	X		An approved molecular test (PCR) will be used. For further detail see Appendix 7 and Section 8.1.3
Columbia Suicide Severity Rating Scale (CSSRS) ²	X		
Height, Weight, Body Mass Index (BMI)	X		
Vital signs	X	X	
12 Lead ECG	X	X	TriPLICATE ECGs will be used to determine participant eligibility at screening
Pregnancy Test	X	X	Follow up test may be obtained up to 37 days post last dose
Urine drug/alcohol/cotinine screen	X		Performed at the standard practice of the site
Hepatitis B surface antigen (HbsAg), Hepatitis C (HCV), Human immunodeficiency virus (HIV) tests ³	X		If test otherwise performed within 3 months prior to first dose of study intervention, testing at screening is not required
Haematology/Chemistry/Urine tests	X	X	Laboratory procedures may be repeated and additional tests may be performed, if needed, at the discretion of the investigator.
Serious Adverse Event (SAE) Review	X	X	All SAEs will be collected from screening visit until the follow up visit
AE Review		X	All AEs will be collected from start of intervention until follow up visit
Concomitant Medication Review	X	X	

¹ In a pandemic situation see [Appendix 7](#)²For early discontinuation that occurs prior to discharge from unit, SARS-CoV-2 testing, CSSRS, and final follow up assessments will be performed. For early discontinuation that occurs post discharge from unit, only final follow up assessments will be performed.³ HIV Ab/Ag 4th generation test (point of care test or laboratory immunoassay)

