Participants in Part 1 will have a screening visit within 28 days prior to the first dose and a follow-up visit approximately 28 days after the last dose. Flexibility of visit scheduling may be required if a pandemic situation applies (see [Appendix 7](#)). Otherwise, study assessments will be performed as indicated in the [SoA](#). Study participants will be confined to the clinic from Day -2 until discharge. Additional outpatient visits will be required on Days 9, 12 and 16. Duration of study participation in Part 1 may be a minimum of approximately 27 weeks for SAD treatment periods 1 to 3. However, in Part 1, study duration will be extended up to approximately 31 weeks to evaluate a higher dose (800 mg) for participants included in this dose period. Participants who have completed Part 1 may be able to re-enroll to complete 800 mg treatment period. To ensure safety, participants will need to go through re-eligibility assessments.

Part 1 SAD: Dose Escalation

Dose escalation in Part 1 will be determined by the Dose Escalation Committee (VH/GSK study team and the PI) based on the double-blind (sponsor-unblinded) safety data and the PK data from the current and previous dose(s) according to the dose escalation charter. Dose escalation will generally not exceed approximately 3-fold between doses up to approximately the predicted minimally effective dose and will not exceed 2-fold thereafter. However, if after the first SAD dose, the exposures are significantly different from the predicted level, the second dose or the sample collection

schedule will be re-estimated and a different fold increase may be used. Post-dose safety and PK data through Day 16 from a minimum of 4 participants receiving VH3739937 are required for dose escalation in Part 1. Dose escalation will be guided by safety as well as the SAD PK stopping criteria (see Section 7.1.4).

Due to the alternating dosing periods between Cohort 1 and Cohort 2, a participant in either cohort will receive the next dose after approximately 3 or 4 weeks.

Study design details Part 2 (MAD):

Part 2 consists of approximately 4 ascending repeat-dose cohorts (Cohorts 3 to 6), each with 10 participants who will receive a once-daily dose of VH3739937 or placebo (PBO) for 14 days (Cohort 3 [25 mg] and Cohort 4 [50 mg]), or for 18 days (Cohort 5 [100 mg]) or three oral doses at weekly intervals over two weeks (Cohort 6 [500 mg]).

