7. DISCONTINUATION OF STUDY INTERVENTION AND PARTICIPANT DISCONTINUATION/WITHDRAWAL

7.1. Discontinuation of Study Intervention

A participant may be withdrawn from the study at any time:

- At his or her own request
- At the discretion of the Investigator in consultation with the Study Sponsor Medical Monitor for safety (including lab abnormalities or intercurrent illness), psychiatric, compliance, or administrative reasons.
- Emergence of any positive (abnormal) response confirmed by the investigator or a clinician (or qualified designee) administered CSSRS during the on-treatment phase (MAD only).
- \geq Grade 3 AE (or clinically significant laboratory abnormality) suspected to be related to VH3739937
- A SAE, regardless of its severity, that is considered be clinically significant and reasonably attributable to dosing with VH3739937, in the opinion of the Investigator.
- A grade ≥ 2 rash with concurrent fever with or without concurrent elevations in liver biochemistry reasonably attributable to dosing with VH3739937, in the opinion of the Investigator.
- Termination of the study by the Sponsor. Safety data will be reviewed by the Sponsor in-stream by single case and collectively. If a safety concerns arises, a decision about continuation of the study will be made.
- Loss of ability to freely provide consent due to incarceration or involuntary treatment of either a psychiatric or physical (eg, infectious disease) illness
- Unblinding of unauthorized Site Staff, including the PI, for any reason

- Repeat non-adherence by the participant with the requirements of the protocol or treatment (as determined by Investigator in consultation with the Study Sponsor Medical Monitor)
- Pregnancy (Section 10.4.3)
- PK stopping criteria is met (Section 7.1.4)
- Clinical criteria for stopping study is met (Section 7.1.5)

If the participant withdraws consent for disclosure of future information, the Sponsor may retain and continue to use any data collected before such a withdrawal of consent. If a participant withdraws from the study, he/she may request destruction of any samples taken and not tested, and the investigator must document this in the site study records.

If a participant chooses to withdraw from the study, he/she will complete a follow-up visit as per [SoA](#).

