7.1.2. QTc Stopping Criteria

The QTcF *must* be used for *each individual participant* to determine eligibility for and discontinuation from the study. This formula may not be changed or substituted once the participant has been enrolled.

The QTcF stopping criteria is based on averaged QTcF values of triplicate electrocardiograms obtained over a brief (e.g., 5-10 minute) recording period.

A participant that meets either bulleted criterion based on the average of triplicate ECG readings will be withdrawn from study treatment.

- QTcF >500 msec,
- Change from baseline: QTcF >60 msec

See the [SoA](#) for data to be collected at the time of intervention discontinuation and follow-up and for any further evaluations that need to be completed.

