7.2. Participant Discontinuation/Withdrawal from the Study

- A participant may withdraw from the study at any time at his/her own request, or may be withdrawn at any time at the discretion of the investigator for safety, behavioural, compliance or administrative reasons. This is expected to be uncommon.
- At the time of discontinuing from the study, if possible, an early discontinuation visit should be conducted, as shown in the [SoA](#). Please see SRM for further detail.
- Please see [SoA](#) for data to be collected at the time of study discontinuation if occurs prior to discharge from unit, and if study discontinuation occurs post discharge from unit, and follow-up and for any further evaluations that need to be completed.
- If the participant withdraws consent for disclosure of future information, the sponsor may retain and continue to use any data collected before such a withdrawal of consent.

- If a participant withdraws from the study, he/she may request destruction of any samples taken and not tested, and the investigator must document this in the site study records.

7.3. **Lost to Follow Up**

- Participants will be expected to be resident in the Phase I unit as per [SoA](#). A participant will be considered lost to follow-up if he or she repeatedly fails to return for scheduled visits and is unable to be contacted by the study site.
- The following actions must be taken if a participant fails to return to the clinic for a required study visit:
 - The site must attempt to contact the participant and reschedule the missed visit as soon as possible and counsel the participant on the importance of maintaining the assigned visit schedule and ascertain whether or not the participant wishes to and/or will continue in the study.
 - Before a participant is deemed lost to follow up, the investigator or designee must make every effort to regain contact with the participant (where possible, 3 telephone calls and, if necessary, a certified letter to the participant's last known mailing address or local equivalent methods). These contact attempts should be documented in the participant's medical record.
 - Should the participant continue to be unreachable, he/she will be considered to have withdrawn from the study with a primary reason of lost to follow-up.

8. **STUDY ASSESSMENTS AND PROCEDURES**

- Study procedures and their timing are summarized in the [SoA](#)

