8.2.1. Time Period and Frequency for Collecting AE and SAE Information

- All SAEs will be collected from the signing of the informed consent form until the follow-up visit at the time points specified in the [SoA](#). However, any SAEs assessed as related to study participation (e.g., study intervention, protocol-mandated procedures, invasive tests, or change in existing therapy) or related to a ViiV/GSK product will be recorded from the time a participant consents to participate in the study.
- All AEs will be collected from the start of intervention until the follow-up visit at the time points specified in the [SoA](#)
- Medical occurrences that begin before the start of study intervention but after obtaining informed consent will be recorded on the Medical History/Current Medical Conditions section of the case report form (CRF) not the AE section.
- All SAEs will be recorded and reported to the sponsor or designee immediately and under no circumstance will this exceed 24 hours, as indicated in [Appendix 3](#).
- The investigator will submit any updated SAE data to the sponsor within 24 hours of it being available. For further detail, please see [Appendix 3](#)
- Investigators are not obligated to actively seek AEs or SAEs after the conclusion of the study participation. However, if the investigator learns of any SAE, including a death, at any time after a participant has been discharged from the study, and he/she considers the event to be reasonably related to the study intervention or study participation, the investigator must promptly notify the sponsor.

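### Participants who stop early get only the final follow-up assessments, so those stopped for toxicity lose the scheduled 192, 264 and 360 h checks while drug is still present

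*Protocol*

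**What the plan says.** **Schedule for early stoppers.** Protocol Section 1.2, Table 1, footnote 2 has two rules. A participant who discontinues in the unit has SARS-CoV-2 testing, CSSRS and the final follow-up assessments. For one who has already left: "For early discontinuation that occurs post discharge from unit, only final follow up assessments will be performed". The follow-up column of Table 1 holds a physical examination, vital signs, ECG, laboratory tests and AE review. The table has no PK row.

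**Stopping drug and leaving the study.** Section 7.1 is titled as discontinuation of study intervention, but its list opens with "A participant may be withdrawn from the study at any time". It includes toxicity reasons, among them an event at or above "Grade 3 AE (or clinically significant laboratory abnormality) suspected to be related to VH3739937". Section 7.1.2 differs: a participant meeting the QTc criteria "will be withdrawn from study treatment". It still refers to the Schedule of Activities for the data to collect.

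**Timing.** Section 7.2 says "At the time of discontinuing from the study, if possible, an early discontinuation visit should be conducted, as shown in the" Schedule of Activities. Table 1 places the follow-up about 28 days after the last dose. Section 8.2.1 says "All AEs will be collected from the start of intervention until the follow-up visit".

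**The visits at issue.** For Part 1, Section 4.1 says "Additional outpatient visits will be required on Days 9, 12 and 16". Tables 2 to 6 set matching visits in every part at 192, 264 and 360 h after the last dose. The amendment rationale ties them to a half-life longer than anticipated, along with safety review and operational reasons. The synopsis gives the value: "Due to the observed half-life of ~90 h".

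**The concern.** AEs, laboratory values, vital signs and ECGs are primary endpoints in all three parts. The late visits exist largely because drug persists much longer than predicted. A participant who completes dosing has them. One who is stopped for toxicity has no stated right to them, although that participant has also been dosed and is still clearing drug.

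Scheduled observation is then thinnest where a safety signal has already appeared. A second event, such as a new laboratory or ECG change in the days after a stop, would be found only if it caused symptoms or someone chose to look. This matters most in Cohort 5, whose 18-day duration was chosen to reveal early hypersensitivity reactions. Planned concentrations during washout, which would help relate exposure to the event, are lost as well.

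**Working it through.** **Inputs.**
- Half-life about 90 h (protocol Sections 1.1 and 4.1); about 24 h was predicted (Section 4.3.1).
- One-compartment model with first-order elimination (Section 2.2.1).
- Discharge at 120 h and outpatient visits at 192, 264 and 360 h after the last dose (Tables 2 to 6).
- Follow-up at about 28 days, i.e. 28 × 24 = 672 h (Table 1).

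**Reproducing the plan's own figure.** The protocol expects accumulation of about 6-fold with daily and 1.3-fold with weekly dosing. With R = 1/(1 − 2^(−τ/t½)) and t½ = 90 h:
- Daily, τ = 24 h: R = 5.93, which matches.
- Weekly, τ = 168 h: R = 1.38 at steady state and 1.35 after the three planned doses, close to the stated value.

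**Why the late visits matter.** At the predicted 24 h, discharge at 120 h falls 120/24 = 5 half-lives after dosing. At 90 h it falls only 120/90 = 1.3 half-lives after, and five half-lives take 5 × 90/24 = 18.75 days.

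**Drug remaining after the last dose**, as 2^(−t/t½). The range 70 to 110 h is an assumption, used to test sensitivity.

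| Time after last dose | t½ = 70 h | t½ = 90 h | t½ = 110 h |
|---|---|---|---|
| 120 h (discharge) | 30.5% | 39.7% | 47.0% |
| 192 h | 14.9% | 22.8% | 29.8% |
| 264 h | 7.3% | 13.1% | 19.0% |
| 360 h | 2.8% | 6.3% | 10.4% |
| 672 h (28 days) | 0.1% | 0.6% | 1.5% |

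At 90 h, 39.7 − 6.3 = about 33% of the decline falls between 120 and 360 h, the stretch these three visits cover. A single visit at 28 days sees almost no drug.

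**Which sentence of footnote 2 applies.** All dosing is in the unit, and in Part 2 discharge follows the last dose. A Part 2 participant taken off drug is therefore under the in-unit sentence. The sentence quoted above covers people who leave after discharge, including between periods in Parts 1 and 3. Neither sentence keeps the 192 to 360 h visits.

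**How the SAP treats the data.** SAP Appendix 4 counts an AE as treatment-emergent up to 22 days after the stop date, i.e. 22 × 24 = 528 h. The three late visits fall inside that window; a visit at 672 h falls outside. Early stoppers stay in the Safety population, so they share a denominator with completers but have fewer scheduled checks inside the window. SAP Appendix 5 leaves unscheduled visits out of summary tables and figures. Extra ECG or laboratory results recorded that way would appear only in listings.

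**The case against.** The strongest reply is that safety follow-up does not stop, and this stands:
- The investigator remains responsible for AEs that led to discontinuation (Section 8.2), and SAEs are followed to resolution or stabilisation (8.2.3).
- Clinically significant laboratory abnormalities are repeated until they settle (8.1.5).
- Liver stops are monitored weekly or twice weekly, and Appendix 5 has a PK-sample provision.
- Unscheduled safety samples (1.2) and up to 10 additional PK samples (8.4) are allowed.

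For a known event this can be denser than three outpatient visits. It does not replace a fixed set of checks for events not yet known, and the extra sampling is discretionary.

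A second reply is that Section 7.1 is permissive and the QTc and liver rules stop treatment only. On that view, someone who stops drug but stays in the study keeps the late visits, whose hours count from the last dose. That is a reasonable reading, but no text states it, and Section 7.1.2 sends treatment-only stops to the same schedule. Some stops do require leaving: unblinding (6.4) and a confirmed positive CSSRS response (2.3.1).

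A reader might infer that every toxicity trigger forces study withdrawal. The permissive lead-in and the treatment-only rules do not support that. A reader might also infer that observation ends on the day of stopping. Table 1 places follow-up about 28 days after the last dose, and Section 7.1 gives those who choose to withdraw a follow-up visit. The wording of 7.2 leaves the timing ambiguous; it does not establish an immediate end.

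Safety analysis is descriptive, the event that prompts a stop is recorded, and escalation needs a minimum number of active participants with data through Day 16, 29 or 33. A shortened case therefore cannot silently fill that minimum. These points limit the harm. Section 7.2 also refers to the study reference manual, which is not among the documents.

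**Conclusion.** The point holds in limited form. Footnote 2 is a stated rule, and nothing in the protocol keeps the 192, 264 and 360 h visits for a dosed participant who stops early. At a half-life of about 90 h, roughly 23%, 13% and 6% of the level remains at those times, and 0.6% at 28 days. What is lost is scheduled detection of new events and planned exposure data during that tail. It would go too far to say that safety observation ceases or that the exposure-event relation is lost altogether: PK up to the stop is kept, later samples are permitted and known events are followed.

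The percentages assume first-order decline at the stated half-life. Over 70 to 110 h, 15% to 30% remains at 192 h, so the conclusion does not depend on the exact value. The number of participants affected is unknown and probably small. This is a should-fix item, not a must-fix.

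**What to change.** In Sections 7.1 and 7.2 and in Table 1 footnote 2:
- Separate stopping study intervention from withdrawing from the study. The stopping criteria themselves stay unchanged.
- State that any dosed participant who stops and does not withdraw consent keeps the 192, 264 and 360 h visits and the 28-day follow-up, all counted from the actual last dose.
- Reserve the immediate early-discontinuation visit for those who decline further visits. This also settles the timing of the final follow-up.

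In the data specifications, label the retained visits by hours after the last dose, so that they are summarised as planned and not listed as unscheduled. For example, after a last dose on Day 10 the 192 h visit falls on Day 18, not on Day 22 as for Cohort 3 and 4 completers.

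The cost is a few sentences of protocol text and some already defined outpatient visits for the few who stop early.
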